#### **4.0 PRETREATMENT EVALUATIONS/MANAGEMENT**

Note: This section lists baseline evaluations needed before the initiation of protocol treatment that do not affect eligibility.

##### **4.1 Required Evaluations/Management**

- 4.1.1 Neurocognitive assessments within 2 weeks before starting modified whole-brain radiotherapy (WBRT-HA/SIB): HVLT-R, COWAT, TMT, MOS, MMSE.
- 4.1.2 Fatigue assessment within 2 weeks before starting WBRT-HA/SIB: the Multidimensional Fatigue Inventory (MFI-20).
- 4.1.3 Scans Prior to WBRT-HA/SIB: See Section 6.0 for details.
- 4.1.4 Subjects will be screened for renal impairment prior to administration of gadolinium-based contrast agents (GBCA) as it is routinely done in the Radiology Department at UT Southwestern. A creatinine determination 28 days prior to the research MRI examination must be available to calculate an eGFR. An eGFR calculation may be repeated closer to the MRI appointment if the patient's medical condition has changed. An eGFR  $\geq 45$  mL/min/1.73m^2 is considered acceptable for administration of a standard weight-based dose of GBCA for research purposes.

#### **5.0 REGISTRATION PROCEDURES**

##### **5.1 Procedures**

- 5.1.1 Enrolling investigator must review eligibility checklist and sign/date at bottom that all criteria have been met.
- 5.1.2 FAX or carry the enrollment form to the Registrar
- 5.1.3 A unique patient participation ID will be assigned
- 5.1.4 Eligibility will be confirmed by CRO Personnel
- 5.1.5 Successful completion of preregistration activities will be confirmed by the CRO Personnel
- 5.1.6 Treatment assignments will be conveyed to the treating investigator

## 6.0 RADIATION THERAPY

Note: Intensity-Modulated RT (IMRT) is required. Acceptable IMRT modalities include LINAC-based IMRT involving static gantry angles or volumetric arc therapy (VMAT).

### 6.1 Dose Specifications (see target definitions below)

- 6.1.1 Prescription dose will be according to the following specifications:
  - 6.1.1.1 The prescription for the whole brain planning target volume (PTVwb - whole brain clinical target volume excluding the hippocampal avoidance regions) is 20 Gy in 10 fractions. Treatment will be delivered once daily, 5 fractions per week, over 2 to 2.5 weeks. Breaks in treatment should be minimized.
  - 6.1.1.2 The prescription dose for each metastasis planning target volume (PTV1, PTV2, etc.) is 40 Gy in 10 fractions as a simultaneous integrated boost.
  - 6.1.1.3 Coverage is considered adequate when 95% of each of the PTVs is covered by the assigned prescription dose (D95% = prescription dose).
  - 6.1.1.4 The minimum dose to 98% of each of the PTVs (D98%) is 80% of the assigned prescription dose.

### 6.2 Technical Factors

- 6.2.1 Megavoltage equipment capable of delivering static intensity modulation with a multileaf collimator or dynamic intensity modulation (using a multileaf collimator) is required. The use of custom-made compensators or partial transmission blocks is also acceptable as long as dose specifications and constraints are satisfied.
- 6.2.2 A megavoltage beam of 4 MV or greater must be used, with a minimum source-axis distance of 80 cm.
- 6.2.3 MRI  
T1 contrast enhanced images should be used for targeting of gross lesions. T2 images may also be used when they allow clear demarcation of the edge of the targeted tumor(s). These imaging sequences should be obtained within two weeks of initiating treatment.

### 6.3 Localization, Simulation, and Immobilization

- 6.3.1 Patients will be immobilized in the supine position using an immobilization device such as an Aquaplast mask over the head. A pituitary board may be utilized to maximize the number of available vertex beams. Patients will be treated in the immobilization device.
- 6.3.2 A non-contrast treatment-planning CT scan of the entire head region with a 1.25 mm slice thickness will be required to define clinical and planning target volumes and hippocampal avoidance regions. The treatment-planning CT scan must be acquired with the patient in the same position and immobilization device as for treatment. This should be obtained within 2 weeks of initiating treatment.
- 6.3.3 The MRI (see Section 6.2.3) and treatment-planning CT should be fused semi-automatically for hippocampal contouring.

### 6.4 Target Volumes

- 6.4.1 The Whole Brain Clinical Target Volume (CTVwb) is defined as the whole brain parenchyma to C1 (if no posterior fossa metastasis) or C2 (if MRI evidence of posterior fossa metastasis).
- 6.4.2 The Whole Brain Planning Target Volume (PTVwb) is defined as the CTV excluding the hippocampal avoidance regions (see Section 6.5.2).
- 6.4.3 Each brain metastasis identified on MRI will be assigned a unique Clinical Target Volume identified by number (CTV1, CTV2, etc.)
- 6.4.4 Each metastasis Planning Target Volume (PTV1, PTV2, etc.) is defined as the corresponding CTV with a uniform 2 mm margin.

### 6.5 Critical Structures

- 6.5.1 Bilateral hippocampal contours will be manually generated on the fused 3D-SPGR MRI-planning CT image set by the treating physician according to contouring instructions.
- 6.5.2 Hippocampal avoidance regions will be generated by three-dimensionally expanding the hippocampal contours by 5 mm.
- 6.5.3 The lenses and orbits will be contoured as per the clinical experience of the treating physician. Care should be taken to minimize the dose to the lens and orbits.

**6.6 Documentation Requirements**

- 6.6.1 Verification orthogonal films or images are required. For all forms of IMRT dose delivery, orthogonal films or images that localize the isocenter placement shall be obtained. The length of the treatment field shall be indicated on these films.

**6.7 Final Quality Assurance Analysis**

- 6.7.1 All final treatment plans and contours will be reviewed after initiation of WBRT-HA/SIB.
- 6.7.2 If unacceptable deviations of MRI/CT fusion, hippocampal contours, and/or WBRT-HA/SIB IMRT planning are found on final quality assurance analysis, that patient will be rendered inevaluable on final data analysis.
- 6.7.3 If a patient has an unscheduled break exceeding 3 normally scheduled treatment days, this unacceptable deviation must be reported to the Principle Investigator, and the patient will be considered inevaluable on final data analysis.

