**6.8 Compliance Criteria and Critical Structure Constraints**

Treatment Component	Parameter	Per Protocol	Variation Acceptable	Deviation Unacceptable
Contouring	Hippocampal Contouring	≤ 2 mm deviation using the Hausdorff distance*	> 2, ≤ 7 mm deviation using the Hausdorff distance*	Neither per protocol or variation acceptable
Planning	PTVwb	D95 ≥ 20 Gy; D98 ≥ 16 Gy	D95 ≥ 18 Gy; D98 ≥ 15 Gy	Neither per protocol or variation acceptable
	PTV1r, PTV2r, etc	D95 ≥ 40 Gy; D98 ≥ 30 Gy	D95 ≥ 37.5 Gy; D98 ≥ 28 Gy	Neither per protocol or variation acceptable
	Hippocampus	Maximum Dose ≤ 16 Gy	Maximum Dose ≤ 17 Gy	Maximum dose > 17 Gy
Unscheduled Break Days		0 break days	1-3 break days	> 3 break days

\* To assess the Hausdorff distance, the Principal Investigator will remotely contour the “true” hippocampus on the submitted MRI/CT fusion, and a comparison will be made to the submitted contours.

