### 13.2 Sample Size

The primary endpoint will be delayed recall, as measured by the relative (percent) change in HVLTR delayed recall score from the start of treatment to 3 months after the start of treatment.

The sample size calculation will address the specific primary hypothesis that WBRT-HA/SIB reduces decline in delayed recall (from baseline to 3 months). We do not expect improvement in delayed recall; at best, we anticipate a preservation of delayed recall. Data from a randomized trial showed that the decline in HVLTR delayed recall score was 64% at 4 months for those getting whole brain radiation for brain metastases (Chang et al., 2009). We anticipate that WBRT-HA/SIB will have better delayed recall functioning at 3 months than WBRT alone. Detecting a 30% average relative loss due to WBRT-HA/SIB suggests a 50% relative improvement over previous results. The null and alternative hypotheses are:

$$H_0: \Delta HVLTR = 0.60 \text{ vs. } H_A: \Delta HVLTR \leq 0.30$$

$\Delta$ HVLT-R is the mean of relative decline between baseline and 3 month after treatment in this patient population. For patient individual i, the relative decline is calculated as follows:  $\Delta$ HVLT-Ri = ( HVLT-Ri0 - HVLT-Ri3 ) / HVLT-Ri0 , where HVLT-Ri0 and HVLT-Ri3 denote individual patient scores at baseline and 3 months after treatment, respectively.

Initial sample size calculation:

Based on the one-sided one sample t-test, assuming a standard deviation of 41%, with alpha=0.05 (one-sided), a total of 9 analyzable patients would ensure 80% statistical power to detect a 30% average relative loss in delayed recall at 3 months. Assuming a death rate of 60% prior to 3 months and a 10% in-evaluable rate, the target sample size will be 34 registered patients.

Sample size re-estimation based on internal pilot study:

The internal pilot consists of 32 patients enrolled at baseline, among which 9 patients have complete information on HVLT-R delayed recall score at the start of treatment and 3 months after the start of treatment. For the 9 patients, the mean and standard error of relative (percent) change (decline) in HVLT-R delayed recall score is 31% and 51%. We re-estimate the required sample size using the updated standard error.

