Based on the one-sided one sample t-test, assuming a standard deviation of 51%, with alpha=0.05 (one-sided), a total of 18 analyzable patients would ensure 80% statistical power to detect a 30% average relative loss in delayed recall at 3 months. Assuming a death rate of 60% prior to 3 months and a 10% in-evaluable rate, the target sample size will be 50 registered patients. Therefore, additional 18 patients need to be recruited at the second stage.

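### Plans and contours are reviewed only once treatment has begun, with no deadline or correction step, so a patient can be treated on an unacceptable plan and then dropped from the analysis

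*Combined protocol and SAP*

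**What the plan says.** Section 6.7.1 of the protocol: "All final treatment plans and contours will be reviewed after initiation of WBRT-HA/SIB". Section 6.7.2: if that review finds unacceptable deviations of fusion, hippocampal contours or IMRT planning, "that patient will be rendered inevaluable on final data analysis".

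The limits are in the 6.8 table. For example, a hippocampal contour more than 7 mm from the reference by Hausdorff distance, or a hippocampal maximum dose above 17 Gy, is unacceptable. The footnote to that table explains the reference: "the Principal Investigator will remotely contour the “true” hippocampus on the submitted MRI/CT fusion". It gives no timing. The contours used for treatment come from the treating physician (6.5.1): "Bilateral hippocampal contours will be manually generated on the fused 3D-SPGR MRI-planning CT image set by the treating physician according to contouring instructions".

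Before treatment, Section 5.1 covers eligibility and registration: "Successful completion of preregistration activities will be confirmed by the CRO Personnel". Sections 6.3 to 6.6 and Appendix I list imaging, contouring, planning and isocenter images, but no review of the plan or contours. Section 13.2 sizes the trial with "a 10% in-evaluable rate" and does not break that rate down by cause.

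**The concern.** The trial tests a treatment whose content is its geometry. By 6.5.2 the avoidance region is the hippocampal contour plus 5 mm, and by 6.4.2 the whole-brain target is the brain outside that region. A contour error beyond the 7 mm limit is larger than the whole 5 mm margin. Where the submitted contour misses true hippocampus by that distance, the missed tissue falls in the volume planned for whole-brain dose. The 6.8 table does not say on which contour the hippocampal maximum dose is read, so a check read on the submitted contour could still pass.

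Two things are at stake. First, a patient may receive fractions on a plan outside the protocol's own limits, and delivered fractions cannot be taken back. Second, the response is to remove the patient from the analysis. Because the review has no deadline and nothing says the reviewer is blinded to outcome, that removal could be decided after the 3-month delayed-recall score is available. In an analysis of about 18 patients, one or two such decisions could matter.

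**Working it through.** **1. Does the check need data that exist only after treatment starts?**

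| Component | Input | Available before first fraction? |
|---|---|---|
| Fusion | Planning MRI and CT (6.2.3, 6.3.2, 6.3.3) | Yes |
| Hippocampal contour | Treating physician's contour (6.5.1) and the Principal Investigator's reference contour on the same fusion (6.8 footnote) | Yes, if the reference is drawn then |
| Target and hippocampal dose limits | Dose values of the final plan (6.8) | Yes |
| Break days | Delivered treatment (6.7.3, 6.8, 6.9.2) | No |

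Only break days require a review after treatment has begun.

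**2. The plan's own sample size.** Inputs from 13.2: null 0.60, alternative 0.30 (difference 0.30), SD 0.51, one-sided alpha 0.05, power 80%, 60% deaths before 3 months, 10% inevaluable.

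- n = (SD × (z0.95 + z0.80) / difference)² = (0.51 × (1.645 + 0.842) / 0.30)² = 17.87, so 18. This reproduces the plan.
- Registered: 18 / (0.40 × 0.90) = 50. This also reproduces.
- The 18 rests on the normal approximation (power 80.3%). For the t-test that 13.3.1 specifies, exact noncentral-t power is 77.3% at n = 18, 79.4% at 19 and 81.3% at 20.

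**3. How many patients can an earlier check recover?** Section 13.2 reports 32 patients already enrolled in the internal pilot and 18 still to recruit. A change to 6.7.1 can act only on those 18.

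- Upper limit, if all inevaluability were planning error: 18 × 0.40 × 0.10 = 0.72 patients. From a base of 18 this gives 18.72, with exact-t power about 79% (between the values at 18 and 19).
- If half were planning error: 0.36 patients, n = 18.36, power about 78%.
- If none were: no change, 77.3%.

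**4. The same, using the pilot's actual yield.** The pilot gave 9 complete patients of 32 (28.1%, against the planned 0.40 × 0.90 = 36%).

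- Without the change: 9 + 18 × 0.36 = 15.5 evaluable, power about 71%.
- With the full recovery: 9 + 18 × 0.40 = 16.2 evaluable, power about 73%.

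Exact-t power stays below 80% in every case.

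**The case against.** The strongest objection is that the text says less than the concern needs. Section 6.7.1 says after initiation, not after completion. Treatment lasts long enough for an early review to fall mid-course (6.1.1.1: "Treatment will be delivered once daily, 5 fractions per week, over 2 to 2.5 weeks"). The heading speaks of a final analysis, which might imply an earlier check that was not written down. The 6.8 limits are known to the planners, who can test their own dose values in advance. So a reader might infer that errors are always found too late, or that no earlier check takes place; the documents establish neither. A reader might also infer that every plan gets a central check by a named reviewer. Section 6.7.1 names no reviewer, and the only task assigned is the Principal Investigator's reference contour. All of this stands. It does not remove the point: no deadline, correction step or earlier review is written, and exclusion is the only stated outcome.

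A second tempting inference is that an earlier check would bring power to 80% with no added patients, by raising 18 evaluable patients to 20. That would require applying it to all 50, and 32 are already enrolled.

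A third is that most of the 10% is planning error. The documents do not say so. Breaks (6.7.3, 6.9.2), discontinuation (11.7) and missed tests are other routes; Section 1.5 cites compliance above 78% at one month in one earlier trial and 77% to 87% at 6 months in another. The planning share could be near zero.

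Finally, nothing shows that any exclusion has been or would be influenced by outcome. The plan merely leaves that possible.

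**Conclusion.** The point holds as one of procedure. The protocol schedules its plan and contour check after treatment has begun, sets no deadline, provides no correction and excludes the patient on failure, when the inputs would allow the same check beforehand. This rests on the documents' silence about any earlier review; if one exists in practice, writing it into 6.7 resolves the matter.

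The benefit is fidelity to the treatment under test, safety, and closing off exclusions decided after the outcome may be known. The benefit for power is negligible: between 0 and about 0.7 evaluable patients, or exact-t power between 77.3% and about 79% on the plan's own rates. That range assumes 60% deaths and 10% inevaluable among the 18 remaining patients. The shortfall against 80% has other causes and would remain.

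**What to change.** Amend 6.7.1 so that, for all remaining patients, the existing fusion, contour and plan check against the 6.8 criteria is completed before the first fraction, with unacceptable plans corrected and re-checked. State who performs it and record its date. Keep the later review for delivered treatment, such as break days, and require its evaluability decision to be made without sight of the 3-month score. The check also needs one set of limits. Section 6.1.1.4 puts D98 for each metastasis at 80% of prescription (0.80 × 40 = 32 Gy) while the 6.8 table gives 30 Gy, and the break limit is 3 days in 6.7.3 but 7 in 6.9.2; these passages must be reconciled.

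The cost is time. MRI and planning CT should both fall within two weeks of starting treatment (6.2.3, 6.3.2), so reference contouring, comparison and any re-planning must fit in that window and could cause a short scheduling delay. The documents give no turnaround figure, so this burden cannot be sized. The criteria and materials are those already in the protocol; whether extra reviewer time is needed depends on who does the review now, which 6.7.1 does not say.

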**6.8 Compliance Criteria and Critical Structure Constraints**

Treatment Component	Parameter	Per Protocol	Variation Acceptable	Deviation Unacceptable
Contouring	Hippocampal Contouring	≤ 2 mm deviation using the Hausdorff distance*	> 2, ≤ 7 mm deviation using the Hausdorff distance*	Neither per protocol or variation acceptable
Planning	PTVwb	D95 ≥ 20 Gy; D98 ≥ 16 Gy	D95 ≥ 18 Gy; D98 ≥ 15 Gy	Neither per protocol or variation acceptable
	PTV1r, PTV2r, etc	D95 ≥ 40 Gy; D98 ≥ 30 Gy	D95 ≥ 37.5 Gy; D98 ≥ 28 Gy	Neither per protocol or variation acceptable
	Hippocampus	Maximum Dose ≤ 16 Gy	Maximum Dose ≤ 17 Gy	Maximum dose > 17 Gy
Unscheduled Break Days		0 break days	1-3 break days	> 3 break days

\* To assess the Hausdorff distance, the Principal Investigator will remotely contour the “true” hippocampus on the submitted MRI/CT fusion, and a comparison will be made to the submitted contours.

**6.9 Radiation Therapy Interruptions**

- 6.9.1 Radiotherapy will be continued without interruption if at all possible.

- 6.9.2 If the sum total of radiotherapy interruptions exceeds -7 normally scheduled treatment days, the treatment will be considered an unacceptable deviation from the protocol. This should be reported to the Principal Investigator, and the patient will be considered inevaluable on final data analysis.

## 6.10 Radiation Therapy Adverse Events

### 6.10.1 Definition of an Adverse Event (AE)

- 6.10.1.1 Any unfavorable and unintended sign (including an abnormal laboratory finding), symptom, or disease temporally associated with the use of a medical treatment or procedure regardless of whether it is considered related to the medical treatment or procedure (attribution of unrelated, unlikely, possible, probable, or definite).

### 6.10.2 Definition of a Serious Adverse Event (SAE)

- 6.10.2.1 Any adverse experience occurring during any part of protocol treatment and 30 days after that results in any of the following outcomes:
- Death;
  - A life-threatening adverse experience;
  - Inpatient hospitalization or prolongation of existing hospitalization;
  - A persistent or significant disability/incapacity;
  - A congenital anomaly/birth defect.

### 6.10.3 Expected Adverse Events

- 6.10.3.1 Acute, < 90 days from treatment start: Expected adverse events include hair loss, erythema of the scalp, head ache, nausea and vomiting, lethargy, and transient worsening of neurologic deficits. Reactions in the ear canals and on the ear should be observed and treated symptomatically.

- 6.10.3.2 Late, > 90 days from treatment start: Possible adverse events include radiation necrosis, cognitive dysfunction, visual difficulties, accelerated atherosclerosis, and radiation-induced neoplasms.

- 6.10.4 Any adverse event equivalent to CTC V.4 grade 3, 4, or 5 or which precipitates hospitalization or prolongs an existing hospitalization must be reported regardless of designation (expected or unexpected) along with the attribution. This includes all deaths that occur within 30 days after the patient was discontinued from the study regardless of attribution AND any events that occur beyond 30 days and are considered probably related to treatment.

- 6.10.5 SAE reports must be completed (the CRF plus information describing the event, the grade, and the attribution) within 48 hours of the investigator's awareness of the occurrence of the event.

- 6.10.6 Attribution of an event can be categorized as:

- Not Related
- Possibly Related
- Probably Related
- Definitely Related

- 6.10.7 Adverse events (below grade 3) do not need to be submitted immediately. Rather, they should be documented in the Adverse Events Clinical Report Form (CRF) along with a brief description of the event, grade, and attribution).

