## **12.0 DATA COLLECTION**

### Summary of Data Submission

Item	Due
Demographic Form	Within 2 weeks of registration
Initial Evaluation Form	
Mini-Mental Status Exam	
Neurocognitive Evaluation Summary Form (HVLTR, TMT, COWAT)	Before the first treatment
Fatigue Evaluation Summary, FACT-BR, EQ-5D	
Follow-up Forms	3, 6, 9, 12, and 24 months after radiotherapy is completed
Mini-Mental Status Exam	
Neurocognitive Evaluation Summary Form (HVLTR, TMT, COWAT)	
Fatigue Evaluation Summary	
Quality of life Assessments (FACT-BR, EQ-5D)	As above
Progression MRI Scan & Report	Within 1 week of scan date

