### 13.2 Procedures

13.2.1 Clinical trials are assessed for safety on a continual basis throughout the life of the trial. All SAE's and any AEs that are unexpected and possibly/likely related to study participation are reported to UTSW IRB through an electronic research system per UTSW IRB guidelines.

All clinical trials are reviewed on monthly basis for enrollment. All local SAEs are reviewed by Radiation Oncology DSMC monthly for severity and attribution. For investigator-initiated trials, all SAEs at affiliated institutions are monitored as local SAEs. The principle investigator and study coordinator will present a study treatment summary and SAEs for review. Source documents will be available for the DSMC members during the review. NCI Common Toxicity Criteria Version 4 will be used for grading and attributing adverse events.

If the SAE occurs on a multi-institutional clinical trial coordinated by the Radiation Oncology Clinical Research Office, the Clinical Research Manager or primary coordinator ensures that all participating sites are notified of the event and resulting action, within one (1) working day of the determination.

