**APPENDIX I:**

STUDY PARAMETER TABLE	Pre-Treatment			Follow-Up					
	Within 5 yrs prior to registration	Within 28 days prior to registration	Within 2 wks prior to registration	Before 1 st treatment	3 mos after RT	4-6 mos after RT	9 mos after RT	12 mos after RT	24 mos after RT
Histo/cyto eval	X								
History/physical		X			X	X	X	X	X
Performance status		X			X	X	X	X	X
Serum creatinine		X							
Serum pregnancy test (if applicable)			X						
Adverse event eval					X	X	X	X	X
MRI with contrast and assessment		X			X	X	X	X	X
Head CT simulation scan				X					
HA/SIB-WBRT treatment planning				X					
Neurocognitive assessment				X	X	X	X	X	X
Fatigue assessment				X	X	X	X	X	X
Quality of Life Assessments				X	X	X	X	X	X

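### No scheduled adverse-event evaluation falls within the plan's own acute window, so lower-grade acute events depend on unscheduled recording

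*Combined protocol and SAP*

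**What the plan says.** Section 6.10.3.1 sets the acute period as "Acute, < 90 days from treatment start" and lists the effects expected in it, among them hair loss, scalp erythema, headache, nausea and lethargy. Section 6.1.1.1 gives the length of the course: "Treatment will be delivered once daily, 5 fractions per week, over 2 to 2.5 weeks".

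In Appendix I the row "Adverse event eval" is empty in every column before follow-up. It has five marks, one for each follow-up visit, and the first is 3 months after radiotherapy. The calendar has no column for visits during treatment, at its end, or at one month. The data-submission table in Section 12.0 agrees: follow-up forms are due "3, 6, 9, 12, and 24 months after radiotherapy is completed". That table does not name the adverse-event form or give it a due date of its own.

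Other sections provide for reporting outside the calendar. Section 6.10.4 makes every grade 3, 4 or 5 event, and every event that causes or prolongs hospitalization, reportable whether expected or not. Section 6.10.5 allows 48 hours from awareness for a serious adverse event report. Section 6.10.7 sends events below grade 3 to the adverse-event case report form without urgency and without naming a visit or interval. The Data Safety Monitoring Plan adds continual safety assessment and monthly committee review of local serious events.

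The sample-size section carries this premise: "Assuming a death rate of 60% prior to 3 months and a 10% in-evaluable rate".

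**The concern.** The protocol separates acute from late toxicity at 90 days from the start of treatment, yet its calendar makes the first planned enquiry about adverse events after that point. Evaluating adverse events is secondary objective 2.2.6, and it is not confined to serious ones. If no one is scheduled to ask about events while they are occurring, the acute profile of the boost regimen depends on spontaneous entries and on what patients remember months later. Patients who die before the first visit cannot contribute even that recall, and the plan expects them to be the majority.

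**Working it through.** **1. Is the 60% death rate a working assumption of the plan?** Section 13.2 inflates 18 analyzable patients for 60% deaths and 10% inevaluable:

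18 / ((1 − 0.60) × (1 − 0.10)) = 18 / 0.36 = 50.

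This is the stated target, so the 60% is the figure on which enrolment was planned.

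**2. When is the first scheduled evaluation?** Day from treatment start = length of radiotherapy + 3 months, compared with day 90.

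- Length of radiotherapy: 11 days (ten weekday fractions starting on a Monday) to 17.5 days (2.5 weeks × 7).
- Three months: 90 to 91.3 days. As a generous alternative, 12 weeks = 84 days.

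| Reading | Day from start | Relative to day 90 |
|---|---|---|
| After radiotherapy, shortest | 11 + 90 = 101 | 11 days after |
| After radiotherapy, longest | 17.5 + 91.3 = 108.8 | about 19 days after |
| After radiotherapy, 12 weeks, shortest course | 11 + 84 = 95 | 5 days after |
| From treatment start, as for the primary endpoint | 90 to 91.3 | 0 to about 1 day after |

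The acute definition is strictly under 90 days, so each of these falls outside it.

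**3. How many patients would have died by then?** On the plan's assumption, 0.60 × 50 = 30 die before 3 months and 20 remain alive.

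The internal pilot does not settle the true rate. Complete primary data were available in 9 of 32 (28%), against the 36% (0.40 × 0.90) that the plan assumes evaluable. Deaths before 3 months in the pilot can therefore be at most 23 of 32 (72%) and may be far fewer, because death is not separated from other reasons for missing data.

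**4. What covers the period before the first visit?**

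| Event | Route | Scheduled time point before day 90 |
|---|---|---|
| Grade 3 to 5, or hospitalization | Mandatory report (6.10.4) | None; depends on awareness |
| Serious event in treatment or the next 30 days | Report within 48 hours of awareness (6.10.2, 6.10.5) | None; depends on awareness |
| Below grade 3 | Case report form entry (6.10.7) | None, and no interval given |

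The period in the serious-event definition ends at about day 41 (11 + 30) to day 47.5 (17.5 + 30). From there to the first visit is about 60 days (90 − 30 = 60; 91.3 − 30 = 61.3) with no scheduled contact. The grade 3 to 5 rule still applies in that interval. Lower grades have only the case report form.

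**The case against.** The strongest reply is that recording is not tied to calendar visits. Patients attend for ten daily fractions. Section 6.10.3.1 asks for ear reactions to be observed and treated, and Section 11.7.1 requires documentation when treatment stops for an unacceptable adverse event. Both presuppose that staff watch for toxicity during treatment. Severe events must be reported whenever they become known, and a death is itself a grade 5 event. A reader might infer from the calendar that acute toxicity goes systematically unrecorded, or is collected only by recall from survivors. The documents do not support that: Sections 6.10.4, 6.10.5 and 6.10.7 and the monitoring plan all provide for unscheduled recording. The reply stands for severe events. For lower grades it shows that recording is possible, but not when anyone is to ask.

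The timing is also less clear-cut than one figure suggests. Sections 13.1.1 and 13.2 count the 3-month assessment from treatment start, which puts it at the edge of the window, and a 12-week reading on that anchor would give day 84, just inside. But the adverse-event row is headed by time after radiotherapy, and even day 84 would be a single look at the end of the period.

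A reader might also infer that late reporting is restricted, because Section 6.10.4 mentions "any events that occur beyond 30 days and are considered probably related to treatment". That does not follow. The 30 days there run from discontinuation from the study, the preceding sentence has no time limit, the clause adds to it, and the calendar schedules evaluations to 24 months. Nor must that clause match the monitoring plan's "any AEs that are unexpected and possibly/likely related to study participation are reported to UTSW IRB", which is a separate rule for reporting to the review board. The most that can be said is that *probably related* does not literally include *definitely related*.

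Finally, the 60% is an assumption, not observed mortality, and sits uneasily with the life-expectancy criterion of at least 3 months in Section 3.1.6. The calendar gap does not depend on it; the count of 30 does.

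**Conclusion.** The point holds as a gap in scheduled ascertainment. On the calendar's own anchor the first adverse-event evaluation comes 11 to 19 days after the acute window closes. On the primary endpoint's anchor, with 3 months taken as 90 to 91 days, it comes at day 90 to 91.

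The weakness lies in events below grade 3, where many of the listed expected effects may fall. Under-ascertainment is likely there, and greatest in patients who die early: about 30 of 50, conditional on the plan's 60%. Its size cannot be calculated from the documents. Missed events would lower the reported frequency if all treated patients form the denominator, but Section 13.3.2.5 names no denominator and no split between acute and late.

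The consequence is confined to a descriptive secondary objective, and severe events have cover. It merits correction but does not threaten the primary analysis.

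**What to change.** - Add an adverse-event evaluation to Appendix I at treatment visits that patients already attend, for example mid-course and last fraction. Optionally add one telephone check before day 90.
- List the adverse-event form with due dates in the Section 12.0 table, and state whether the 3-month visit counts from the start or the end of radiotherapy.
- In Section 13.3.2.5, summarise acute events over all treated patients, including those who die before 3 months.
- As a small clarification, say that the last clause of Section 6.10.4 also includes events judged definitely related.

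The cost is one or two extra forms and possibly a short call per patient. No clinic visit is added and treatment is unchanged. For patients already treated, acute events can be reviewed only from existing records, so any summary should distinguish them from patients followed under the revised calendar.
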